3.2 Secondary Objectives

The secondary objectives of the study are:

1. To assess the Verified Detection Rate (VDR) for M1 disease of rhPSMA-7.3 (¹⁸F) PET findings (as determined by central BIE) on a patient level in patients with newly diagnosed unfavorable intermediate-, high-, or very high-risk PCa using histopathology or confirmatory imaging.
2. To assess the VDR for M1 disease of rhPSMA-7.3 (¹⁸F) PET findings (as determined by central BIE) on a patient level in patients with negative conventional imaging.
3. To assess the positive predictive value (PPV) of rhPSMA-7.3 (¹⁸F) PET for N1 and M1 lesions (as determined by central BIE) compared to histopathology or confirmatory imaging (M1 lesions only).
4. To assess the PPV of rhPSMA-7.3 (¹⁸F) PET for detecting pelvic LN metastases compared to surgical pathology on a patient level in which a FP patient is defined as having at least one FP region (right or left pelvis), regardless of any coexisting TP findings.
5. To assess the negative predictive value (NPV) of rhPSMA-7.3 (¹⁸F) PET for detecting pelvic LN metastases compared to surgical pathology on a patient level in which a FN patient is defined as having at least one FN region (right or left pelvis), regardless of any coexisting TN findings.
6. To assess the impact of rhPSMA-7.3 (¹⁸F) PET BIE on a) upstaging patients planned for RP or b) converting planned RP to EBRT.
7. To determine the inter- and intra-reader agreement of rhPSMA-7.3 (¹⁸F) scan interpretation by blinded independent readers.
8. To assess the safety of rhPSMA-7.3 (¹⁸F) injection in patients.

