5.2 Secondary Endpoints

The secondary endpoints for this study will be:

1. Percentage of patients in whom rhPSMA-7.3 (¹⁸F) imaging detects at least one verified M1 metastasis, as determined by central BIE.
2. Percentage of patients with negative conventional imaging for M1 disease in whom rhPSMA-7.3 (¹⁸F) PET detects at least one verified M1 metastasis, as determined by central BIE.
3. Patient level PPV of rhPSMA-7.3 (¹⁸F) PET BIE for N1 and M1 lesions compared to histopathology or confirmatory imaging (M1 lesions only).
4. PPV of rhPSMA-7.3 (¹⁸F) PET for detecting pelvic LN metastases compared to surgical pathology on a patient level in which a FP patient is defined as having at least one FP region (right or left pelvis), regardless of any coexisting TP findings.
5. NPV of rhPSMA-7.3 (¹⁸F) PET for detecting pelvic LN metastases compared to surgical pathology on a patient level in which a FN patient is defined as having at least one FN region (right or left pelvis), regardless of any coexisting TN findings.
6. a) The percentage of patients being upstaged to N1 or M1 disease;
b) The percentage of patients in whom planned RP is converted to EBRT.
7. Kappa statistic for the agreement between and within blinded independent readers on the interpretation of rhPSMA-7.3 (¹⁸F) scans.
8. Safety (AEs, vital signs clinical laboratory evaluations, 12-lead ECG and focused physical examinations) of rhPSMA-7.3 (¹⁸F) injection in patients.

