*** The patient should receive treatment within 45 days (may be extended up to 60 days due to the COVID-19 pandemic) post-IP administration, with treatment decision based on rhPSMA-7.3 (¹⁸F) PET imaging and conventional imaging (see k below).

a To include medical history and concomitant disease record, including a history of PCa, diagnosis date and prior PCa treatments, as well as histological confirmation of adenocarcinoma of the prostate.

b Pre-IP administration.

c Vital signs to be recorded pre-IP administration and post-IP administration.

d To be performed pre-IP administration.

e If not already performed within 60 days prior to screening, conventional imaging will be performed as part of routine clinical practice, which may include bone scan (^{99m}Tc-HDP, ^{99m}Tc-MDP), abdominal/pelvic CT or MRI, and chest CT as per local practice). Note: Conventional imaging that has been performed at non-participating institutions will be accepted provided the scans are retrievable and reviewed by the participating institution. Note: baseline conventional imaging performed as part of routine clinical practice should be performed at least 24 hours prior to the investigational rhPSMA-7.3 (¹⁸F) PET scan.

f Baseline blood safety laboratory tests, including hematology (full blood count), biochemistry (urea and electrolytes, liver function tests) and coagulation to be performed pre-IP administration.

g AEs will be monitored and recorded from the time of informed consent until the last study visit.

h For full details see the Study Imaging Manual.

- i To discuss imaging results and further procedures/treatments with the patient (all patients).
- j If rhPSMA-7.3 (¹⁸F) PET does not detect M1 disease, the patient will undergo the scheduled RP and PLND. In patients without M1 lesions identified and in whom the patient and physician believe, after obtaining the results of the rhPSMA-7.3 (¹⁸F) PET, that EBRT would be a better therapeutic option than RP, the patient may proceed to EBRT and the rationale for this change of management will be documented on the eCRF.

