2.2 Secondary Objective(s)

The secondary objectives of the study are:

1. To assess the Verified Detection Rate (VDR) for M1 disease of rhPSMA-7.3 (¹⁸F) PET findings (as determined by central BIE) on a patient level in patients with newly diagnosed unfavorable intermediate-, high-, or very high-risk PCa using histopathology or confirmatory imaging.
2. To assess the VDR for M1 disease of rhPSMA-7.3 (¹⁸F) PET findings (as determined by central BIE) on a patient level in patients with negative conventional imaging.
3. To assess the positive predictive value (PPV) of rhPSMA-7.3 (¹⁸F) PET for N1 and M1 lesions (as determined by central BIE) compared to histopathology or confirmatory imaging (M1 lesions only).
4. To assess the PPV of rhPSMA-7.3 (¹⁸F) PET for detecting pelvic LN metastases compared to surgical pathology on a patient level in which a FP patient is defined as having at least one FP region (right or left pelvis), regardless of any coexisting TP findings.
5. To assess the negative predictive value (NPV) of rhPSMA-7.3 (¹⁸F) PET for detecting pelvic LN metastases compared to surgical pathology on a patient level in which a FN patient is defined as having at least one FN region (right or left pelvis), regardless of any coexisting TN findings.
6. To assess the impact of rhPSMA-7.3 (¹⁸F) PET BIE on a) upstaging patients planned for RP or b) converting planned RP to external beam radiation therapy (EBRT).

PAREXEL International

Blue Earth Diagnostics
BED-PSMA-301

Statistical Analysis Plan

7. To determine the inter- and intra-reader agreement of rhPSMA-7.3 (¹⁸F) scan interpretation by blinded independent readers.

8. To assess the safety of rhPSMA-7.3 (¹⁸F) injection in patients.

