4.10 Biopsy/Surgery

If the rhPSMA-7.3 (¹⁸F) PET shows M1 metastatic disease, the patient will be asked to undergo a biopsy or confirmatory imaging of the PET-positive lesion(s) to confirm the presence of a metastasis. If a surgical intervention of this lesion is carried out as part of the treatment, this may substitute for a biopsy. If the patient has proven M1 metastatic disease, the disease management may be altered, based on the responsible physician's clinical judgement. This change in disease management will be documented on the eCRF.

If rhPSMA-7.3 (¹⁸F) PET does not detect M1 disease, the patient will undergo the scheduled RP and PLND. In patients without M1 lesions identified and in whom the patient and physician believe, after obtaining the results of the rhPSMA-7.3 (¹⁸F) PET, that EBRT would be a better therapeutic option than surgery, the patient may proceed to EBRT and the rationale for this change of disease management will be documented on the eCRF.

PAREXEL International

Blue Earth Diagnostics
BED-PSMA-301

Statistical Analysis Plan

The regional PLND must be performed by a suitably qualified surgeon and should include, at minimum, resection of lymphatic tissue for histological analysis from the following nodal groups: 1) hypogastric (internal iliac), 2) external iliac, and 3) obturator LNs. Extended LN dissection may be performed if clinically appropriate and the anatomical regions (e.g. presacral, common iliac, peri-rectal) with left/right designations, should be recorded on the eCRF. The location of the dissected material shall be marked in order to allow matching with their anatomical origin (left and right pelvis); the left and the right side of the specimen shall be clearly marked. The dissected LNs will be sectioned and analyzed by a pathologist for the presence or absence of PCa according to standard of care at the clinical site. The number of lymph nodes sampled and found positive for PCa will be registered and summarized.

Patients with PET M1 will be summarized using the EEP by confirmatory method(s), result of confirmation, change in disease management, surgery (radical prostatectomy and pelvic lymph node dissection) performed, Lymph node dissection and (additional) treatment received. All counts will be presented including percentage of patients categorized as PET M1.

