4.14.3.6 Upstaging

- a) The percentage of patients being upstaged to N1 or M1 disease;*
- b) The percentage of patients in whom planned RP is converted to EBRT.*

The endpoints will be calculated as follows:

- Upstaging to N1 = Proportion of patients with positive BIE PET finding by BIE and negative conventional imaging finding from local investigator in pelvic lymph nodes, out of all the patients with evaluable scans.
- Upstaging to M1 = Proportion of patients with positive BIE PET finding and negative conventional imaging finding from local investigator in other (extra-pelvic) areas, out of all the patients with evaluable scans.

PAREXEL International

Blue Earth Diagnostics
BED-PSMA-301

Statistical Analysis Plan

- Planned RP converted to EBRT = Proportion of patients with positive BIE PET finding and planned RP changed to EBRT by local investigator, out of all the patients with evaluable scans.

4.14.3.7 Kappa statistic for the agreement between and within blinded independent readers on the interpretation of rhPSMA-7.3 (¹⁸F) scans.

This analysis concerns all EEP patients.

For this analysis, the patient's categorization to positive or negative by the blinded readers will be used, in pelvic lymph nodes and in extra-pelvic region.

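### Endpoint 6b counts changes from planned prostatectomy to EBRT in BIE-positive men without using the recorded reason or naming a lesion site, so it does not measure the impact of the PET

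*Protocol*

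**What the plan says.** **Objective.** Secondary objective 6 (Protocol 3.2, SAP 2.2) concerns the impact of the PET BIE on upstaging or on "converting planned RP to EBRT".

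**Endpoint label.** Protocol 5.2 gives 6b as "The percentage of patients in whom planned RP is converted to EBRT", with no condition on the PET result or the reason.

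**Operational definition.** SAP 4.14.3.6, third bullet, defines it as "Proportion of patients with positive BIE PET finding and planned RP changed to EBRT by local investigator, out of all the patients with evaluable scans". SAP Section 1 gives the SAP precedence where the two documents differ, so this is the rule that will be programmed.

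**Reason for change.** Protocol Appendix 1, footnote j, applies to men in whom no M1 lesion is identified and in whom EBRT is judged the better option once the PET result is known: "the patient may proceed to EBRT and the rationale for this change of management will be documented on the eCRF". Protocol 9.1.7 says the same, and SAP 4.10 repeats it: "the patient may proceed to EBRT and the rationale for this change of disease management will be documented on the eCRF".

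**Who acts on which read.** Under Protocol 9.1.6 and 11.5, the site's local read is what is reported and discussed with the patient. The three central reads serve the efficacy endpoints.

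**The concern.** The objective is about cause, but the numerator records only that two things are true of the same man: a central reader called something positive, and his planned RP became EBRT. The study has a single arm, so there is no comparison group to show how many men would have changed plan anyway. Appendix 1 schedules the planned-treatment and change-of-plan item only in the follow-up column, so it provides no separate record of the plan between baseline imaging and the PET. The documented reason is therefore the most direct evidence of attribution, and the definition of 6b leaves it out.

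The condition on PET positivity is also loose. The two upstaging bullets tie the finding to pelvic lymph nodes or to extra-pelvic areas; the EBRT bullet names no site. At stake is whether a reported 6b percentage can be described as impact of the PET.

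**Working it through.** **1. No figure to reproduce.** The documents give no expected rate, power or test for 6b. SAP 4.14.3 makes the secondary efficacy variables descriptive apart from the kappa analysis. The stated 90% powers belong to the co-primary endpoints and do not depend on 6b.

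**2. Is the reason used elsewhere in the SAP?** SAP 4.10 summarises change in disease management for PET M1 patients, whereas footnote j's EBRT route is for men without M1 lesions. For PET M0 patients it summarises surgery and treatment received. SAP 4.14.3 summarises and lists the patient pathway. None of these is described as broken down by reason. The table and listing shells are not among the documents, so a listing of the reason cannot be ruled out.

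**3. What the site-free filter admits.** Prostate is one of the PET reading categories in SAP 4.9. The men are treatment-naive with confirmed adenocarcinoma (Protocol 6.1), and Protocol Section 2 says PSMA is over-expressed in most prostate cancers. If prostate uptake counts as positive, the filter may exclude few men. That is an inference; the documents give no rate of prostate positivity.

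**4. Which conversions are counted.** Classify every RP-to-EBRT conversion by recorded reason and by BIE result:

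| Recorded reason | BIE positive | BIE negative |
|---|---|---|
| PET result | A: counted | L: not counted |
| Other | B: counted | D: not counted |

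With N men with evaluable scans:

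- 6b as written = (A + B)/N
- PET-attributed conversion = (A + L)/N
- Difference = (B − L)/N

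L exists because the physician acts on the local read while the filter uses the central one. The difference is positive if B exceeds L and negative if L exceeds B.

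**5. Illustration.** All counts are assumed. N = 375 is planned enrolment standing in for evaluable scans. With A + B = 20, 6b as written is 20/375 = 5.3% (exact 95% CI 3.3 to 8.1).

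| A | B | L | PET-attributed (A + L)/375 | 6b as written |
|---|---|---|---|---|
| 15 | 5 | 0 | 15/375 = 4.0% (2.3 to 6.5) | too high |
| 10 | 10 | 0 | 10/375 = 2.7% (1.3 to 4.8) | too high |
| 5 | 15 | 0 | 5/375 = 1.3% (0.4 to 3.1) | too high |
| 10 | 10 | 10 | 20/375 = 5.3% | equal |
| 10 | 10 | 15 | 25/375 = 6.7% | too low |

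With A + B = 40 and L = 0, 10.7% (7.7 to 14.2) becomes 8.0%, 5.3% or 2.7% when 75%, 50% or 25% of the reasons name the PET.

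**6. Analysis set.** SAP 4.14 makes the Efficacy Analysis Population (EAP) the default for efficacy. SAP 4.5 requires RP and PLND for entry to it. A man treated with EBRT in place of RP is not in the EAP, so under the default A + B is zero by construction. The denominator of all patients with evaluable scans suggests that something wider is meant. The Extended Efficacy Population (EEP) would fit, but SAP 4.5 assigns it to M1-related efficacy and kappa, and the 6b bullet names no set.

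**The case against.** **The SAP already filters on PET positivity.** This is correct. A reader might infer that every conversion, whatever its cause, counts as PET impact. Under the SAP, conversions in BIE-negative men are not counted. The problem is confined to cells B and L.

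**Conversion is written as a decision made after the PET.** Footnote j does open the EBRT route only once the PET result is known. That fixes the order of events and makes PET influence plausible, but it does not establish the reason in a given man. The protocol asks for the rationale to be recorded for that purpose.

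**Footnote \*\*\* shows that baseline imaging drives conversions.** A reader might infer this because the footnote bases treatment on "PET imaging and conventional imaging (see k below". The cross-reference leads to footnote k, which concerns confirmation of suspected M1 disease. The imaging meant may therefore itself follow from the PET, and the text draws no link to baseline conventional imaging.

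**The COVID-19 extension to 60 days implies conversions through surgical delay.** The extension allows more time for surgery. Nowhere do the documents name delay as a reason for EBRT.

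**The error favours the sponsor.** The documents do not support a direction. Cell B inflates 6b, cell L deflates it, and a literal EAP analysis would drive it to zero.

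**Other data bear on attribution.** Reads by location, baseline imaging results and the pathway listing do help, so the recorded reason is not the only evidence. None of them states why the plan changed.

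**A numerator based on the site's reason departs from an objective about the BIE.** This has force. However, the plan routes the local read, not the BIE, to the treating physician, so the decision itself is informed by the local read. Showing the BIE-positive subset beside the main figure keeps the link to the objective.

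**Conclusion.** The point holds for SAP 4.14.3.6, third bullet. The reason for each change to EBRT is collected, the definition of 6b does not use it, and the filter names no lesion site. The result mixes conversions prompted by the PET with others in BIE-positive men, and misses those prompted by a local-positive, BIE-negative scan. Read literally, the figure is a conversion rate among men with a positive central read, not a measure of impact.

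The size cannot be determined: the error is (B − L)/N, and the documents give none of the three quantities. The percentages above rest on assumed counts and show scale only. How permissive the filter is depends on whether prostate uptake counts, which the SAP leaves open.

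The consequence is limited. 6b is a descriptive secondary endpoint, and the co-primary tests are unaffected. The correction is worth making because 6b is the only planned endpoint on conversion to EBRT and the field needed is already collected.

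**What to change.** Amend SAP 4.14.3.6, third bullet, as follows.

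1. Report all RP-to-EBRT conversions among men with evaluable scans, tabulated by recorded reason: PET result, conventional imaging, patient preference, other, not stated. Code the reasons before database lock and without sight of the central reads.
2. Report as PET impact the conversions whose reason names the PET result. Beside it, show the subset with an extra-prostatic BIE-positive finding (pelvic node or extra-pelvic).
3. State that the analysis set is the EEP with evaluable scans, so that the EAP default does not remove converted men.

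The cost is SAP wording and a small amount of coding of one existing field. The reported impact figure may be smaller. A reason recorded by an unblinded site is still not proof of cause, and the report should say so.

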4.14.3.7.2	Intra-reader agreement analysis	30
4.14.4	Exploratory Efficacy Variables	30
4.14.4.1	Diagnostic performance (sensitivity and specificity) of rhPSMA-7.3 (¹⁸ F) PET for detecting pelvic LN metastases compared to surgical pathology on a regional level.	30
4.15	Safety Evaluation	31
4.15.1	Adverse Events	31
4.15.2	Deaths, Serious Adverse Events, and Other Significant Adverse Events	32
4.15.3	Clinical Laboratory Evaluation	32
4.15.4	Vital Signs, Physical Findings and Other Observations Related to Safety	33
4.15.5	Other safety	33
4.15.6	Safety Monitoring (Independent Data Monitoring Committee [IDMC], Data Monitoring Committee [DMC], Data and Safety Monitoring Board [DSMB])	33
4.16	Determination of Sample Size	34
4.17	Changes in the Conduct of the Study or Planned Analysis	34
5	REFERENCES	35
6	Appendix	36
6.1	SAS program to reproduce data in Zhou et al [10].	36

PAREXEL International

Blue Earth Diagnostics
BED-PSMA-301

Statistical Analysis Plan

REVISION HISTORY

Version No.	Effective Date	Summary of Change(s)
1.0	03 July 2020	Finalized document
2.0	18 Aug 2021	
Added BMI
 
Wording: Replaced consensus between blinded readers with majority of blinded readers.
 
Added that within analysis of subcategories, categories with low counts may be collapsed.
 
Removed second exploratory objective and endpoint
 
Updated first exploratory endpoint to use cluster binary data estimation of Confidence Interval

3.0	Date of Last Signature	
Changed TEAE definition from on or before Visit 3 to on or before Day 4.
 
Changed medications and/procedures starting after Day 4 not to be summarized.
 
Changed summaries of TEAE leading to death, serious adverse events, and discontinuation will only display TEAE.

PAREXEL International

Blue Earth Diagnostics
BED-PSMA-301

Statistical Analysis Plan

LIST OF ABBREVIATIONS

Abbreviation / Acronym	Definition / Expansion
AE	Adverse event
BIE	blinded image evaluation
CI	Confidence interval
CSP	Clinical Study Protocol
COVID-19	Coronavirus disease 2019
CT	Computed tomography
DRM	Data Review Meeting
EBRT	External beam radiation therapy
EAP	Efficacy Analysis Population
ECG	electrocardiogram
eCRF	electronic Case Report Form
EEP	Extended Efficacy Population
FAS	Full Analysis Set
FN	False Negative
FP	False Positive
FSP	Full Safety Population
GGG	Gleason Grade Grouping
IP	Investigational product
IMP	Investigational Medicinal Product
IV	Intravenous
LN	Lymph Node
MedDRA	Medical Dictionary for Regulatory Activities
MRI	Magnetic resonance imaging
NPV	Negative Predictive Value
PCa	Prostate Cancer
PET	Positron emission tomography
PLND	Pelvic lymph node dissection
PP	Per Protocol Population

PAREXEL International

Blue Earth Diagnostics
BED-PSMA-301

Statistical Analysis Plan

Abbreviation / Acronym	Definition / Expansion
PPV	Positive predictive value
PSA	prostate-specific antigen
PT	Preferred Term
RP	Radical prostatectomy
SAE	Serious adverse event
SAP	Statistical Analysis Plan
SD	Standard Deviation
SOC	System Organ Class
SOP	Standard Operating Procedures
SoT	Standard of Truth
TEAE	Treatment-emergent adverse event
TLFs	Tables, Listings and Figures,
TN	True Negative
TP	True Positive
VDR	Verified Detection Rate
WHO-DD	WHO Drug Global

PAREXEL International

1 INTRODUCTION

Prostate cancer (PCa) is the most prevalent cancer in men in the developed world and the third leading cause of death (Jemal, 2011). It is most commonly diagnosed in men aged 65 years and over and in its early stages it is largely asymptomatic, with tumors detected by identification of increased levels of prostate-specific antigen (PSA) in peripheral blood. If detected early, and when the disease is organ confined, the 5-year survival rate approaches 100%.

Accurate staging of newly diagnosed PCa assists in directing appropriate treatment strategies. The National Comprehensive Cancer Network (NCCN Guidelines; Version 1.2020; PROS-2) recommend bone imaging and abdominal/pelvic imaging as the initial work-up in patients with newly-diagnosed high- and very high-risk PCa, as well as in a subgroup of patients with unfavorable intermediate-risk PCa. The primary goal of such imaging is to detect extra-prostatic disease (M1: non-regional nodal involvement, bone, or other sites [UICC, TNM Classification of Malignant Tumours]); the identification of which would likely significantly change the planned treatment regimen from locoregional to systemic therapy.

The overwhelming need for improved imaging should focus on the identification of N1 (metastasis in regional node(s)) and M1 disease, which may potentially have a meaningful impact on patient treatment and outcomes. Ideally, a staging technique that detects extra-prostatic disease should: 1) image the whole body, 2) not be limited to the skeleton, and 3) be both sensitive and specific for identifying PCa extent.

This study is designed to assess the performance of rhPSMA-7.3 (¹⁸F) for detecting N1 and M1 disease in patients with newly diagnosed PCa eligible for curative intent, standard of care locoregional therapy, who have elected to undergo radical prostatectomy (RP) with regional pelvic lymph node dissection (PLND). Evaluation of the sensitivity and specificity of rhPSMA-7.3 (¹⁸F) imaging by central blinded image evaluation (BIE) for detecting regional pelvic lymph node (LN) involvement, compared to histopathology, will be performed as the co-primary endpoints. Therefore, only patients who are scheduled to undergo RP and a PLND will be included in this study.

The Statistical Analysis Plan (SAP) details the statistical methodology to be used in analyzing study data and outlines the statistical programming specifications for the Tables, Listings and Figures (TLFs). It describes the variables and populations, anticipated data transformations and manipulations and other details of the analyses not provided in the Clinical Study Protocol (CSP). In case of discrepancies between Study Protocol and SAP the SAP supersedes the Study Protocol.

The SAP will be finalized prior to database lock and describes the statistical analysis as it is foreseen when the study is being planned. If circumstances should arise during the study rendering this analysis inappropriate, or if improved methods of analysis should arise, updates to the analyses may be made.

The analyses described in this SAP are based upon the following study documents:

- Study Protocol, Version 3.0 (July 01, 2020)
- Electronic Case Report Form (eCRF), Version 4.0 (February 8, 2021)

PAREXEL International

Blue Earth Diagnostics
BED-PSMA-301

Statistical Analysis Plan

- Invicro Independent Review Charter (IRC), Version 2.0 (June 18, 2021)
- Invicro Technical Operations Manual Version 4.0 (August 04, 2020)
- Invicro Review Session Methodology: Conventional Imaging Version 1.0 (June 08, 2021)

The following guidance document has been used:

Guidance for Industry and FDA Staff - Statistical Guidance on Reporting Results from Studies Evaluating Diagnostic Tests (13 March 2007)

